The protocol, informed consent form(s), recruitment materials, and all participant materials will be submitted to the IRB for review and approval. Approval of both the protocol and the consent form must be obtained before any participant is enrolled. Any amendment to the protocol will require review and approval by the IRB before the changes are implemented to the study. All changes to the consent form will be IRB approved; a determination will be made regarding whether a new consent needs to be obtained from participants who provided consent, using a previously approved consent form.

1 PROTOCOL SUMMARY

1.1 SYNOPSIS

Title: Vitamin C Infusion for Treatment In Sepsis and Alcoholic Hepatitis
Study Description: It is our long-term goal to identify relevant “druggable” targets for alcoholic hepatitis (AH) and to translate this knowledge in to effective strategies to prevent and treat AH. This proposal will focus on one key area of unmet need in the field i.e. those with alcoholic hepatitis who have active infection and sepsis.

Objectives: We hypothesize that in patients with sepsis and alcoholic hepatitis, a 96-hour infusion of vitamin C (ascorbic acid, AscA, 200mg/kg/24 hours) will improve hepatic function, be well tolerated, and will attenuate biomarkers of inflammation, vascular injury, and encourage fibrinolysis. To assess the efficacy of a 96-hour intravenous vitamin C infusion protocol (200 mg/kg per 24 hours) in patients with established alcoholic hepatitis (AH) and sepsis. In this course of performing this proof of concept phase II trial we will explore three hypotheses:

Hypothesis 1A: Vitamin C infusion will significantly attenuate hepatic dysfunction as measured by the model for end stage liver disease (MELD) score in patients with alcoholic hepatitis and sepsis.

Hypothesis 1B: Vitamin C infusion will be safe and tolerable in patients with alcoholic hepatitis and sepsis.

Hypothesis 1C: Vitamin C infusion will attenuate biomarkers of inflammation (C-Reactive Protein, procalcitonin), vascular injury (Thrombomodulin, Angiopoietin-2), while inducing the onset of a fibrinolytic state (Tissue Factor Pathway Inhibitor).

Endpoints:

Primary Endpoint: Change in MELD score at 96 hours as compared to baseline when compared to placebo.

Secondary Endpoints:

- SOFA Score and components at hours 48, 96, 168
 - PaO₂/FiO₂
 - SpO₂/FiO₂
 - Platelets
 - Total Bilirubin
 - Vasopressor status
 - Glasgow Coma Score
 - Creatinine or Urine Output
- CLIF-SOFA scores and components at hours 48, 96, 168
 - Total Bilirubin
 - Creatinine
 - Renal replacement therapy (yes/no)
 - West-Haven grade for hepatic encephalopathy (HE)
 - INR
 - Mean arterial pressure (MAP)
 - Use of vasopressors (yes/no)
 - PaO₂ or SpO₂
 - FiO₂
 - Use of mechanical ventilation (yes/no)
- Lille score
 - Age
 - Albumin (on admission)
 - Bilirubin (on admission, hour 96, 168)
 - Creatinine (on admission)
 - Prothrombin time (on admission)
- Maddrey Discriminate Function (MDF) at hours 96, 168
 - Prothrombin time (hours 96, 168)
 - Total bilirubin (hours 96, 168)
 - PT control/reference level (assuming 12 seconds)
- Liver enzymes and function tests at hours 48, 96, 168
 - AST, ALT, total bilirubin, alkaline phosphatase, albumin
- MELD-Na Score at hours 48, 96, 168
 - INR, creatinine, bilirubin, sodium
- Documented tolerability at hours 24, 48, 96
 - Need for dose reduction, headache, dizziness, dry mouth, nausea, vomiting, flushing, rash, hypotension, treatment related adverse events
- Documented safety at hours 24, 48, 96
 - QTc Interval (EKG)
 - Crystalluria (Urinalysis with microscopy and pH testing)
- Serum Biomarkers
 - Procalcitonin, C-reactive protein, thrombomodulin, thromboelastography (TEG), Receptor for Advanced

Glycation End Products, Tissue Factor Pathway Inhibitor at study hours 0, 48, 96, 168 (When feasible)

- Ascorbate level at hour 0, 48, 96, 168 (When feasible)
- Need for escalation of support i.e. need for ventilator or pressor support when these are not needed at baseline
- ICU-free days at day 28
- All-cause mortality to day 28 and day 90
- Hospital-free days at day 90

Study Population: A total of 20 adult subjects with alcoholic hepatitis and suspected or documented sepsis will be enrolled in this study. All participants will be enrolled at the Virginia Commonwealth University Health System (VCUHS).

Phase: Phase II

[figure not shown]
Description of Sites/Facilities Enrolling Participants: Subjects will be recruited from the Emergency Department (ED), inpatient medicine unit admitted to the Digestive Health Service (DHS), and Intensive Care Units (ICU) at VCUHS.

[figure not shown]
Description of Study Intervention: Participants will be randomized to receive either intravenous Vitamin C (sterile L-ascorbic acid mixed in 5% dextrose in water) or placebo (5% dextrose in water). Active treatment will continue for 96 hours, discharge from study hospital, study withdrawal, or death, whichever comes first.

[figure not shown]
Study Duration: Years 1-4

[figure not shown]
Participant Duration: 90 days

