1.2 SCHEMA

1.3 SCHEDULE OF ACTIVITIES (SOA)

| Assessments | Hour 0 | Q 24 hrs 1st 7 days or in ICU | Hour 48 | Hour 96 | Hour 168 | Day 28 | Day 90 |
|---|--------------------------|--|---------------------------|---------------------------|----------------------------|--------------------------|--------------------------|
| VS: BP, HR, MAP, RR, Temp., O2 sats, CVP, Glasgow Coma Scale, West-Haven Scale | S | | S | S | S | | |
| Body Weight | S | | S | S | | | |
| Suspected or known site of sepsis | S | | S | S | S | R | R |
| I/Os Total and Urine and urinalysis for crystalluria | S | R | R | R | | | |
| Assessment of Renal Function with serum creatinine, urine output and Use of Dialysis | S | | S | S | S | S | |
| Calculate MELD Score (most study by biostatistician) | S | | S | S | S | | |
| Labs: Arterial Blood Gases, Na+, K+, BUN, Cr, WBC, Hgb, Hct, Platelets, PT/INR | S | | S | S | S | | |
| Bilirubin Total, AST, ALT, ALP, albumin | S | | S | S | S | | |
| Need for Vasopressors or Inotropes: Epi, Nor-epi, Phenylephrine, Vasopressin, Dopamine | S | | S | S | S | | |
| All concomitant medications including: Methylprednisone, Hydrocortisone, N-acetylcysteine, Antibiotics, Thiamine, Albumin | S | | S | S | S | | |
| AE/SAE Assessments | R | | R | R | R | | |
| Blood for Biomarkers and TEG | R | | R | R | R | | |
| ICU Free Days | | | | | | R | |
| Hospital Free Days | | | | | | | R |
| Glucose Monitoring | S | S | S | S | S | | |
| EKG Monitoring | S | R | R | R | | | |
| All-Cause Mortality | | | | | | R | R |

S = Standard of Care
R = Research

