3 OBJECTIVES AND ENDPOINTS

| OBJECTIVES | ENDPOINTS | JUSTIFICATION FOR ENDPOINTS |
|---|--|---|
| Primary | | |
| Vitamin C infusion will significantly attenuate hepatic dysfunction as measured by the model for end stage liver disease (MELD) score | Change in MELD score at 96 hours as compared to baseline when compared to placebo. | MELD score is an independent positive predictor of mortality in patients with AH. |
| Secondary | | |

| OBJECTIVES | ENDPOINTS | JUSTIFICATION FOR ENDPOINTS |
|--|--|---|
| Vitamin C infusion will be safe and tolerable in patients with severe alcoholic hepatitis . | Documented side effects and serious adverse events at hours 24, 48, 96 when compared with hour zero in high dose ascorbic acid versus placebo. | AscA infusion may cause dry mouth, nausea, vomiting, dizziness, headache, flushing, rash, diarrhea. AscA can be excreted from kidney and lead to crystalluria, so will monitor urine pH via urinalysis. Will also monitor EKGs for QTc changes. |
| Secondary | | |
| Vitamin C infusion will attenuate biomarkers of inflammation (C-Reactive Protein, procalcitonin), vascular injury (Thrombomodulin, Angiopoietin-2), while inducing the onset of a fibrinolytic state (Tissue Factor Pathway Inhibitor) | Modulation of available biomarkers | Changes in these biomarkers may provide mechanistic insight into how vitamin C attenuates inflammation |
| Secondary | | |
| Vitamin C Infusion will improve clinical endpoints in this patient population . | 
Change in SOFA Score and Components at hours 48, 96, 168
 
Change in CLIF-SOFA scores and Components at hour 48, 96, 168 when compared to placebo
 
Change in MELD-Na, MDF, Lille scores at hour 48, 96, 168 when compared to placebo
 
Ascorbate level at hour 0, 48, 96, 168 (When feasible)
 
ICU-free days at day 28
 
All-cause mortality to day 28, 90
 
Hospital-free days at day 90
 | CLIF-SOFA, MDF, MELD, and Lille scores are associated with mortality in alcoholic hepatitis. Ascorbate levels are associated with mortality in sepsis patients in the ICU. AH patients have prolonged hospitalizations and are frequently in the ICU. |

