7 STUDY INTERVENTION DISCONTINUATION AND PARTICIPANT DISCONTINUATION/WITHDRAWAL

7.1 DISCONTINUATION OF STUDY INTERVENTION

If subjects do not tolerate the drug due to side effects such as nausea, vomiting, flushing, rash, headache, diarrhea, develops crytalluria on urinalysis, or QTc prolongation >50% baseline, we will reduce the subsequent doses by 50%. If the QTc is greater than 550 msec at any time, the drug will be discontinued.

Loss of indwelling venous/arterial catheter or peripheral intravenous access will also trigger the stopping of Vitamin C infusions but subjects will remain on study. Blood glucose monitoring will continue via the central laboratory for 36 hours after the last infusion via peripheral IV draws or peripheral sticks. Biomarker sampling via peripheral IV and/or peripheral stick is allowable as it occurs only 4 times throughout the study and likely only once (if at all) after the patient has been discharged from the unit and is without a central line.

The study drug will be discontinued if a patient develops a metabolic acidosis unexplained by other etiologies (lactic acidosis secondary to septic shock). Determination of the presence of metabolic acidosis will be made by the clinical care team. Study drug will also be discontinued if primary care team or surrogate decision maker request withdrawal. Data collection will continue on these patients following withdrawal of study drug.

Requests to unblind a patient's study treatment can be made to the study (investigational) pharmacist or clinical care team. Unblinding study treatment should occur only in the case of an emergency when knowledge of the study treatment is essential for subject care to treat a serious adverse event and prevent further harm or death.

If possible, a decision to unblind should be discussed with the Principal Investigator or a sub-Investigator prior to unblinding the study treatment.

If a blind is broken (either intentionally or unintentionally), the circumstances should be documented as to who, what, when, and why and all documentation shall be kept by the study pharmacist.

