- Collection and monitoring of vital signs: blood pressure, temperature, heart rate, oxygen saturation
- Abbreviated physical exam
- Collection of blood for hematology, coagulation, clinical chemistry, biomarkers
- Document urine volume, urinalysis
- 12-Lead EKG
- AE review and reporting

Treatment Day 3 (Hour 72):

- Collection of concomitant medications (if applicable)
- Collection and monitoring of vital signs: blood pressure, temperature, heart rate, oxygen saturation
- Abbreviated physical exam
- Collection of blood for standard of care: hematology, coagulation, clinical chemistry
- Document urine volume
- 12-Lead EKG
- AE review and reporting

Treatment Day 4 (Hour 96):

- Collection of concomitant medications (if applicable)
- Collection and monitoring of vital signs: blood pressure, temperature, heart rate, oxygen saturation
- Abbreviated physical exam
- Collection of blood for SOC hematology, coagulation, clinical chemistry, and biomarkers
- Document urine volume, urinalysis
- 12-Lead EKG
- AE review and reporting

Study Day 7 (Hour 168):

- Collection of concomitant medications (if applicable)
- Collection and monitoring of vital signs: blood pressure, temperature, heart rate, oxygen saturation

- Collection of blood for SOC hematology, coagulation, clinical chemistry, and biomarkers

Study Day 28

- Phone call or chart review to document morbidity and mortality

Study Day 90

- Surviving subjects will be asked to come for a close out visit. However, this population is notorious for compliance issues and if they do not come in a phone call and chart review will be done along with assessment via national death register

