9.4 STATISTICAL ANALYSES

9.4.1 GENERAL APPROACH

Continuous variables will be compared across groups using ANOVA or a Kruskal Wallis ANOVA depending on their distribution. Changes from baseline to time of measurement will be compared by analysis of covariance. Categorical variables will be measured by Fisher's Exact test. Correlations will be assessed by Spearman's coefficient.

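### The QTc and crystalluria safety endpoint leaves out hour 72 and has no per-patient summary, so it misses a finding that appears at hour 72 and clears by hour 96

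*Combined protocol and SAP*

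**What the plan says.** **Endpoint.** The synopsis (1.1) places QTc and crystalluria, and nothing else, under "Documented safety at hours 24, 48, 96". Section 3 defines the safety endpoint as "Documented side effects and serious adverse events at hours 24, 48, 96 when compared with hour zero in high dose ascorbic acid versus placebo", and its justification column cites urinalysis and QTc. The tolerability endpoint in 1.1, which begins "Need for dose reduction, headache, dizziness, dry mouth", uses the same three hours.

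**Measurement.** The schedule (1.3) marks EKG and urinalysis as research procedures in the column "Q 24 hrs 1st 7 days or in ICU". Section 8.1 lists a 12-lead EKG at hours 24, 48, 72 and 96. It lists urinalysis at hours 24, 48 and 96, but only urine volume at hour 72.

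**Dosing.** Section 7.1 says "QTc prolongation >50% baseline, we will reduce the subsequent doses by 50"%, and names crystalluria as a trigger for the same reduction. It adds: "If the QTc is greater than 550 msec at any time, the drug will be discontinued". It also keeps collecting data after study drug is withdrawn.

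**Analysis.** Section 9.4.3 covers adverse events, laboratory tests, vital signs and physical examinations. It has no EKG paragraph. The only text that could reach QTc is general: "Changes from baseline to time of measurement will be compared by analysis of covariance" (9.4.1).

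**The concern.** The readings that make up the endpoint also change the treatment. After a QTc or crystalluria finding, the next reading may be at half dose or off drug, so a single later reading need not show what happened on full dose. An endpoint built on such readings should therefore use every on-treatment reading and count each patient who ever had a finding. This one skips one of the four treatment days, and nothing in the plan defines a worst value or an ever-affected count.

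Hypothesis 1B is a claim of safety and tolerability from 20 patients. At that size, individual patients are the evidence, and one patient missing from the named endpoint matters to how the claim reads.

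**Working it through.** **Step 1. Set the times side by side.**

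| Hour | Named endpoint (1.1, 3) | EKG in 8.1 | Urinalysis in 8.1 | Schedule 1.3, EKG and urinalysis |
|---|---|---|---|---|
| 24 | yes | yes | yes | daily column (no hour 24 column exists) |
| 48 | yes | yes | yes | own column |
| 72 | no | yes | no, volume only | daily column |
| 96 | yes | yes | yes | own column |

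The daily column supplies the hour 24 reading, which is inside the endpoint. During dosing only hour 72 is left out. For EKG that reading is clearly planned. For urinalysis, 1.3 and 8.1 disagree.

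**Step 2. Which findings escape.** A finding at hour 24 or 48 counts at that hour whatever happens later. A finding first seen at hour 72 that persists counts at hour 96. Only one first seen at hour 72 and cleared by hour 96 is missed by all three readings.

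**Step 3. How many that could be.** The plan gives no figure for this endpoint. Its 8 per arm (9.2) is for MELD and reproduces as 2 × [5 × (1.960 + 0.842) / 7.25]² = 7.47, rounded up to 8. Only the enrolled 10 per arm is used here.

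Assumptions, none from the documents: chance h of onset at each daily reading in a patient not yet affected; chance r that it has cleared by the next reading; one finding per patient; no deaths; urinalysis done at hour 72. Per 10 patients:

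- ever affected over four readings: 10 × [1 − (1 − h)⁴]
- missed by hours 24/48/96: 10 × h(1 − h)² × r
- positive at hour 96: 10 × Σ h(1 − h)^k (1 − r)^(3−k), k = 0 to 3

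For h = 10%: ever affected = 10 × (1 − 0.6561) = 3.44. With r = 1, missed = 10 × 0.1 × 0.81 = 0.81, so 3.44 − 0.81 = 2.63 are seen.

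| h | Ever affected | Seen at 24/48/96 (r = 0; 0.5; 1) | Positive at hour 96 (r = 0; 0.5; 1) |
|---|---|---|---|
| 5% | 1.85 | 1.85; 1.63; 1.40 | 1.85; 0.84; 0.43 |
| 10% | 3.44 | 3.44; 3.03; 2.63 | 3.44; 1.48; 0.73 |
| 20% | 5.90 | 5.90; 5.26; 4.62 | 5.90; 2.31; 1.02 |

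The loss is 0 when findings persist. When all clear within a day it is 0.45, 0.81 or 1.28 patients per arm. The hour 96 reading alone can fall well below the number ever affected.

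**Step 4. The two QTc thresholds.** Reading the first as a rise of more than half the baseline value, it is crossed at 1.5 × baseline. This exceeds 550 msec for any baseline above 550 / 1.5 = 366.7 msec (400 gives 600; 440 gives 660). Above about 367 msec, the stop threshold is therefore reached before the reduction threshold.

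**Step 5. Precision.** With 0 of 10 affected, the exact two-sided 95% upper limit is 1 − 0.025^(1/10) = 30.8%. Any by-arm count here is descriptive.

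**The case against.** The best reply is that a patient with an hour 72 finding is not invisible. Hour 72 has its own adverse event review (8.1). All on-study adverse events are documented (8.3.4) and their incidence is tabulated by arm, as are withdrawals due to an adverse event (9.4.3). Need for dose reduction is a named item, and because 7.1 lowers the doses that follow, a reduction made at hour 72 should still show at hour 96. Individual laboratory listings plausibly include urinalysis. The DSMB sees safety data by arm at least every 4 weeks (10.1.6).

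Most of this stands, and it limits the point to the named endpoint. It does not remove the point. No passage requires a QTc or crystalluria finding to be recorded as an adverse event; the sentence turning clinically significant changes into adverse events sits under physical examinations. The dose reduction item does not name a drug stop. A patient who stops drug but stays on study may not count as withdrawn.

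A reader might go further and infer that QTc will be compared as arm averages hour by hour, so that the dosing rules erase the harm and affected patients look recovered at hour 96. The documents do not support this. The covariance sentence in 9.4.1 is general, tabulation by time point is written for vital signs only, and the analysis of QTc and crystalluria is simply not specified. Recovery by hour 96 is a condition, not a consequence of the plan.

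**Conclusion.** The point holds in limited form. The named QTc and crystalluria endpoint omits hour 72, 9.4.3 has no EKG summary, and neither a worst value nor an ever-affected count is defined. Because dosing changes on these readings, a finding confined to hour 72 is missed by the endpoint, although other safety outputs may catch it. Under the assumed rates the loss is 0 to about 1.3 patients per arm; the documents supply neither event rates nor clearance rates.

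The reasoning takes the sentence in 7.1 on continued data collection to cover a QTc stop. It is written beside other stopping reasons, but 4.4 follows all subjects to day 90 and nothing ends assessments for these patients. The change is worth making because it is cheap. It makes events visible; it will not make a difference between arms of 10 statistically significant.

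**What to change.** In 1.1, 3 and 9.4.3, define the endpoint per patient over a fixed window from Dose 1 through hour 96, using all scheduled and unscheduled readings including hour 72. Report by arm:

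- (a) maximum QTc change from hour 0;
- (b) number of patients ever meeting each QTc threshold stated in 7.1, once reconciled;
- (c) number of patients with any new crystalluria.

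Show the number of readings per patient, and flag readings taken after a dose reduction or stop. List readings after hour 96 separately. The window should be fixed because daily readings depend on ICU stay, discharge and death, so a maximum taken to the last available reading would give the arms unequal opportunity.

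Reconcile 1.3 with 8.1 on hour 72 urinalysis, and reconcile the two QTc thresholds in 7.1. Which clinical rule should apply is for the investigators.

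The cost is a few lines of text and one small table. The EKG data are already planned; hour 72 urinalysis depends on the reconciliation. The downside is that a maximum is more variable than a single reading and grows with the number of readings, and with 10 per arm the summary is descriptive only.

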4.2 SCIENTIFIC RATIONALE FOR STUDY DESIGN

The purpose of this study is to assess the efficacy of intravenously infused ascorbic acid therapy for patients with alcoholic hepatitis (AH) and sepsis. By restricting the population to those we believe to have both infection and AH, this study targets a disease process and population that has the highest mortality rate and has been studied in animal models. By focusing on sepsis associated with AH, we have selected a group that has a higher disease burden than AH alone and thus likely to have both increased mortality and an increased opportunity for benefit, including a reduction in hepatic dysfunction and ICU length of stay. In choosing the MELD score as the primary outcome, we will be able to discriminate between hepatic function improvement and risk of mortality. By using secondary endpoints such as CLIF-SOFA, documentation of serious adverse events, and biomarkers of inflammation, vascular injury, and coagulation, as the primary outcomes, we will be able to detect changes in clinical outcomes, assess safety and tolerability of ascorbic acid therapy in alcoholic hepatitis, and potential mechanistic insights that are important for demonstrating proof of concept.

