9.3 POPULATIONS FOR ANALYSES

We will perform the following analyses for the study:

- *Intention-to-Treat (ITT) Analysis Dataset:* all randomized participants
- *Modified Intention-to-Treat Analysis Dataset:* participants who took at least one dose of study intervention and/or have some particular amount of follow-up outcome data
- *Safety Analysis Dataset:* subset of participants for whom safety analyses will be conducted (e.g., participants who took at least one dose of study intervention)
- *Per-Protocol Analysis Dataset:* participants in the full analysis (ITT) set who complied with the protocol sufficiently to ensure that these data would be likely to represent the effects of study intervention and will be the primary analysis for all outcomes

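### Escalation of support counts a death without new ventilator or pressor use as no event, and ICU-free and hospital-free days give death no value, so these secondary comparisons can favour the arm with more deaths or hide the difference

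*Combined protocol and SAP*

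**What the plan says.** The secondary endpoint list in Section 1.1 of the combined protocol and SAP contains four relevant items:

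- "Need for escalation of support i.e. need for ventilator or pressor support when these are not needed at baseline"
- "ICU-free days at day 28"
- "Hospital-free days at day 90"
- "All-cause mortality to day 28 and day 90"

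Many of the neighbouring items carry assessment hours, but escalation carries none. The schedule in Section 1.3 and the table in Section 3 repeat the two day-counts by name and add no scoring rule. Escalation is not in the Section 3 table.

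Section 9.4.1 supplies generic tests: "Continuous variables will be compared across groups using ANOVA or a Kruskal Wallis ANOVA depending on their distribution", and "Categorical variables will be measured by Fisher's Exact test". Nothing in Section 9 says what a patient who dies receives on these endpoints, who is at risk for escalation, or how mortality relates to them. Section 9.3 defines the modified intention-to-treat set as "participants who took at least one dose of study intervention and/or have some particular amount of follow-up outcome data" and makes the per-protocol set primary for every outcome.

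Death is foreseen. Section 4.2 states that "this study targets a disease process and population that has the highest mortality rate", and Section 4.4 lists death among the events that can end treatment before 96 hours.

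**The concern.** For escalation, the rule as written is itself the problem. Death without new ventilator or pressor use falls in the favourable category, so an arm can lower its escalation rate by losing patients early. The at-risk set is also unclear. Section 5.1 admits patients already on vasopressors or invasive ventilation, and the baseline clause can be read as excluding them altogether or as judging each support separately.

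For the two day-counts the problem is an absence. Three scoring rules remain open: count days after death as days out of the unit, leave deaths out, or give death the worst value. They can give different directions for the same patients. If the choice is made after the data are seen, it can decide the direction of two outcomes listed under the Section 3 objective of better clinical endpoints.

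**Working it through.** **The plan's own figure.** No figure is given for these endpoints. The only sample size, in Section 9.2, concerns MELD: a 25% fall from 29 is 7.25 points, and with SD 5, two-sided alpha 0.05 and 80% power, n = 2 × (1.960 + 0.842)² × 25 / 7.25² = 7.5, so 8 per arm. It reproduces and has no bearing on this point.

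**Inputs from the documents.** 10 per arm (Section 9.2); windows of 28 and 90 days (Section 1.1). The documents give no mortality rate, length of stay or escalation rate, so everything else below is assumed.

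**Day-counts, two extra deaths.** Assume survivors spend 8 days in the ICU and 20 in hospital, which gives 28 − 8 = 20 and 90 − 20 = 70 free days. Assume the extra deaths occur in the ICU on day 5. The difference between arms is 2 × (value given to death − survivor value) / 10.

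| Rule for death | ICU-free days | Hospital-free days |
|---|---|---|
| Days after death count as free (23; 85) | 2 × (23 − 20)/10 = +0.6 | 2 × (85 − 70)/10 = +3.0 |
| Deaths left out | 0 | 0 |
| Death scored 0 | 2 × (0 − 20)/10 = −4.0 | 2 × (0 − 70)/10 = −14.0 |

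A plus sign means that the arm with more deaths looks better. The direction under literal counting depends on survivors' stay. If survivors never enter the ICU (28 free days), the same two deaths give 2 × (23 − 28)/10 = −1.0.

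**Day-counts, whole arms.** Take 4 against 2 deaths on day 4, with the same survivors:

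- Literal: ICU-free (6 × 20 + 4 × 24)/10 = 21.6 against (8 × 20 + 2 × 24)/10 = 20.8; hospital-free (6 × 70 + 4 × 86)/10 = 76.4 against (8 × 70 + 2 × 86)/10 = 73.2.
- Deaths left out: 20 against 20; 70 against 70.
- Death scored 0: 12 against 16; 42 against 56.

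**Escalation, same deaths.** Suppose everyone is at risk at baseline, a proportion q of survivors escalate, and a proportion f of those who die are supported first. The rate in an arm with d deaths is [q(10 − d) + f·d]/10. With q = 40% and f = 0:

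- As worded: 0.4 × 6/10 = 24% against 0.4 × 8/10 = 32%. The arm with more deaths looks better.
- Death counted as an event: (2.4 + 4)/10 = 64% against (3.2 + 2)/10 = 52%. It looks worse.
- For q from 30% to 50%: as worded 18–30% against 24–40%; with death as an event 58–70% against 44–60%.

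Subtracting the two arms gives (4 − 2)/10 × (f − q). The wording therefore favours the arm with more deaths only when patients who die are supported less often than survivors. At f = 90% the gap is 0.2 × (0.9 − 0.4) = 10 points against the arm with more deaths, close to the 12 points when death is an event.

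**Simulation.** 10 per arm, assumed mortality 50% against 30%, 5,000 trials per setting, ties not counted, no escalation window applied. Survivors' ICU stay averages about 8 days, with about 12 further hospital days. The entries are the share of trials in which the higher-mortality arm looks better.

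| Endpoint and rule | Share of trials |
|---|---|
| ICU-free, literal; mean time to death 4, 5, 8, 12 days | 61%, 58%, 51%, 42% |
| Hospital-free, literal; same times | 71%, 70%, 67%, 63% |
| Either, deaths left out | 50–52% |
| Either, death scored 0 | 18–21% |
| Escalation as worded; f = 0, 40%, 90% | 57%, 40%, 25% |
| Escalation, death as an event | 20–22% |

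**The case against.** The strongest reply has four parts.

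1. *Deaths without support should be few.* Section 5.2 excludes patients not committed to full support, while allowing those who decline only cardiac resuscitation. This stands as a limit on size. At f = 90% the escalation bias nearly disappears. The exclusion applies at entry, however, and does not ensure that later deaths are preceded by ventilator or pressor use.
2. *Mortality is reported separately.* An imbalance would be visible, but the three comparisons would not be corrected by it.
3. *These are secondary endpoints in a 20-patient proof-of-concept trial whose formal hypothesis concerns MELD.* That is true, and it sets the priority. It does not remove the fault.
4. *Section 9.4.1 already allows a rank test.* With two arms, Kruskal-Wallis is equivalent to the rank-sum test, so no new method is needed. Ranking alone does not settle the scoring, because a literal 23 free days still outranks a survivor's 20. Nor is the case against ANOVA one of leverage, since under literal counting an early death lies close to the survivors.

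A reader might infer that the plan scores death as success on the day-counts. It does not say so: it gives only names, and literal counting is one reading of a missing definition. A reader might also take the distance between a literal 23 or 85 days and a score of 0 as the advantage gained by the worse arm. That distance compares two scoring rules within one arm. The gain between arms is far smaller.

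**Conclusion.** The point holds in a limited form. The escalation rule as written puts unsupported deaths with recoveries, has no window, and leaves the at-risk set unclear. It can favour the arm with more deaths when patients who die are supported less often than survivors, and the bias is small when most are supported first. For ICU-free and hospital-free days the defect is a missing value for death. Depending on the rule adopted, a mortality difference could be reversed, hidden or shown. In the two-extra-deaths example the apparent gain under literal counting is 0.6 and 3.0 days, and for the ICU count its sign changes with survivors' stay. The analysis sets in Section 9.3 also leave room for early deaths to be dropped.

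All sizes rest on assumed mortality, timing of death, length of stay and escalation rates. The documents do not support a claim that these comparisons will be reversed, only that nothing in the plan prevents it. The MELD sample size is unaffected.

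**What to change.** State the following in the statistical section before unblinding:

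- **Escalation:** new ventilator support, new vasopressor support or death, over a stated window. Hour 168 is a natural choice because it is the last scheduled assessment of support. Judge each support against its own baseline status, and report the three components separately.
- **Day-counts:** days alive and out of the ICU to day 28, and days alive and out of hospital to day 90, with death by that day scored 0 or ranked below all survivors. Compare them with the rank test that Section 9.4.1 already allows.
- **Deaths:** report them by arm beside all three endpoints.

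The cost is mainly wording, with two downsides. Escalation becomes a composite, which is why its components need separate reporting. The timing of new support may also need chart review: Section 1.3 schedules vasopressor need only at hours 0, 48, 96 and 168, and Section 1.1 lists ventilation only as a CLIF-SOFA component at hours 48, 96 and 168.
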